## 6.3 Statistical tests

Bioequivalence is assumed if 90% (PK) / 95% (PD) of the test and reference ratio of the primary PK/PD parameters confidence intervals (CIs) fall within the limits of 80%-125%.

## 6.4 Common calculations

For quantitative measurements, change from baseline will be calculated as: (Test value at Visit Day X – Baseline value), where the baseline value is defined as the last non-missing observation taken prior to first exposure to IP.

## 6.5 Software

All analyses will be performed using R Version 4.4.1 or higher. R: A Language and Environment for Statistical Computing. R Foundation for Statistical Computing, Vienna, Austria. <https://www.r-project.org/> [2].

---

**7. Statistical considerations****7.1 Missing data**

Missing safety data will not be imputed for this study. All missing or incomplete safety and PK data, including dates and times, are treated as such.

**8. Output presentations**

Summary tables will be stratified by treatment sequence randomized to, unless otherwise specified.

The templates provided in the separate output templates document describe the format and content for presentation of tables, listings and figures (TLFs).

Categorical variables will be summarized and presented with the following nomenclature: n = frequency and % = percentage. Categories of NOT REPORTED, MISSING, and/or UNKNOWN may be excluded from summaries if null (0)

For continuous variables, data will be summarized with the number of participants (N), arithmetic mean, standard deviation (SD), minimum, median and maximum by treatment group.

All percentages (%) for a specific summary are calculated using the total number of participants included in the relevant analysis population as the denominator, unless otherwise specified. Tables will summarize relevant data from the eCRF.

Data listings will be based on all participants randomized to IP, unless otherwise specified.

**9. Primary endpoint assessments**

For PK and PD analysis, refer to sections 22 and 23, respectively. For safety and tolerability analysis, refer to sections 19, 20 and 21.

**10. Secondary endpoint assessments**

For PK and PD analysis, refer to sections 22 and 23, respectively. For safety and tolerability analysis, refer to sections 19, 20 and 21.

**11. Exploratory endpoint assessments**

For the exploratory endpoint assessments refer to section 24.

**12. Participant disposition and withdrawal****12.1 Variables and derivations**

End of study classifications are defined as follows:

**12.1.1 Screening failure**

Participants for whom informed consent was obtained and documented in writing (i.e. the participant signed an informed consent form), but who were not randomized to IP. Individuals who do not meet the criteria for participation in this study may be rescreened only once, at the discretion of the Investigator.

**12.1.2 Completed treatment**

A participant will have fulfilled the requirements for treatment completion if/when the participant has completed all three treatment periods.

**12.1.3 Early withdrawal**

Participants may withdraw from the study at any time with or without reason. The Investigator also has the right to discontinue or terminate participants from the study in the event of concomitant disease, AEs, or any reason that would benefit the participant. If a participant withdraws from the study for any reason, the study site must immediately notify the clinical monitor. The date and reason for study discontinuation must be recorded in the electronic case report form (eCRF). Participants who discontinue early, irrespective of the reason for discontinuation from the study, will be asked to complete the EOS assessments at the time of the participant's withdrawal, as outlined in the schedule of assessments (*Table 3 in the CSP for NKF-INS(A)-101*).

**12.1.4 Completed study**

A participant will have fulfilled the requirements for study completion if/when the participant has completed all three treatment periods, and the end of study (EOS) visit within 2-11 days after last administration of the IP. The participant will be considered as having "completed study" in the event of the EOS visit occurs outside the scheduled 2-11 days after the last IP administration window.

**12.1.5 Lost to follow-up**

The participant stopped coming for visits and study personnel were unable to contact the participant. In cases in which the participant is deemed lost to follow up, prior to this designation, the Investigator (or designee) must make every effort to contact the participant (e.g., telephone calls, certified letter to the participant's last known mailing address, or local equivalent methods, and efforts to reach the participant's emergency contact). The site will make 3 attempts to regain contact with the participant. These contact attempts must be documented in the participant's medical records.

**12.2 Analysis**

Participant disposition and withdrawals will be summarized and presented in data listings for the screening population set.

The number of participants included in the relevant analysis populations, as well as the number of participants excluded with reasons for exclusion from the relevant analysis populations (Section 5) and protocol violations/deviations will be summarized for the SAF population and listed in data listings for the FAS population.

---

**13. Participant demographics and other baseline characteristics****13.1 Variables and derivations**

The following demographic and other baseline characteristics will be summarized by treatment sequence:

- Age (Years) (Calculated relative to date of informed consent, as provided by the participant and recorded in the eCRF)
- Sex
- Race
- Ethnicity
- Height (cm) at Screening
- Weight (kg) at Screening
- BMI (as collected in the eCRF)

The following demographic and baseline characteristics will be listed:

- The date of written informed consent
- Year of birth

**13.2 Analysis**

Demographic data and other baseline characteristics will be summarized by treatment sequence randomized to for the SAF population and presented in data listings for the screening analysis population.

---

**14. Exposure to IP****14.1 Variables and derivations**

The date of first IP administration will be derived as the first date of dosing from the IP administration eCRF page. As this is a single dose study, the date of the first IP administration will also be the last date of the particular IP's administration.

**14.2 Analysis**

Exposure to IP will be presented in data listings for the SAF populations.

---

**15. IP compliance****15.1 Variables and derivations**

Administration of the study treatment will be supervised by unblinded study site personnel to ensure compliance. An unblinded monitor will periodically review the study records to ensure compliance. Discontinuation for compliance is at the Investigator's discretion and is to be noted in the eCRF.

**15.2 Analysis**

Overall treatment compliance to IP will be summarized for each treatment group for the SAF population and presented in data listings. Dosing administration errors will be listed for the same population, citing the treatment sequence, and treatment concerning the dose error and participant number.

**16. Medical and treatment history****16.1 Variables and derivations**

Medical history will be coded using MedDRA. See the relevant Data Management Plan for details.

Medical history will be recorded at screening. The recorded medical history will be updated, if necessary, at admission to treatment period 1. Investigators should document the occurrence, signs, and symptoms of the participant's preexisting conditions, including all prior significant illnesses. Medical history will include alcohol consumption and smoking history, if applicable.

Illnesses first occurring or detected during the study and/or worsening of a concomitant illness during the study are to be documented as AEs in the eCRF in accordance with Section 12.6 in the CSP of NKF-INS(A)-101 v2.0 06-May-2024. All changes that are not present at baseline or described in the medical history and identified as clinically noteworthy must be recorded as AEs.

**16.2 Analysis**

Medical history will be listed for each participant, by system organ class (SOC) and preferred term, for the FAS population.

**17. Prior, concomitant and other medications****17.1 Variables and derivations**

Prior, concomitant and other medications will be coded using WHODrug Global. See relevant Data Management Plan for details.

Medications taken by or administered to the participant for the period before screening will be recorded in the eCRF as prior medications. Restricted therapies include over-the-counter medication within 7 days or prescription medication within 14 days prior to dosing (apart from vitamin/mineral supplements, occasional paracetamol, thyroid placement, or birth control methods).

Any medication or vaccine (including over-the-counter or prescription medicines, vitamins, and/or herbal supplements) other than NKF-INS(A), US-NovoLog® and EU-NovoRapid® that the participant is receiving at the time of enrolment, or receives during the study, must be recorded in the eCRF as concomitant medications along with:

- Reasons for use.
- Dates of administration including start and end dates
- Dosage information including dose, regimen, route and frequency

Relevant prior concomitant medication given within 3 weeks before screening and all medication given from screening until the EOS visit (within 2-11 days after last administration of the study drug) must be recorded.

The participant must be told to notify the investigational site about any new medications taken after administration of the study treatment. All previous and on study Coronavirus disease 2019 (COVID-19) vaccinations should be recorded in the eCRF.

---

Other than those medications explicitly prohibited (*please refer to Section 8.6.1 in the CSP of NKF-INS(A)-101, v2.0 06-May-2024*), concomitant medication decisions will be left to the discretion of the Investigator.

## 17.2 Analysis

Prior- and concomitant medications will be presented in data listings for each participant, only for the FAS population. All medications captured on the concomitant medications panel of the eCRF will be categorised (prior/concomitant) and listed. Prohibited medications will be identified with an asterisk (\*) in the relevant data listings.

## 18. Adverse events

### 18.1 Variables and derivations

Adverse Events (AEs) will be coded using MedDRA. See the relevant Data Management Plan for details.

Treatment-emergent adverse events (TEAEs) are defined as AEs that started at the time of, or after the first IP administration as well as those events that started prior to the first study drug administration, but which worsened after the first study drug administration.

Imputations will only be performed where at least the year is provided. The imputations derived for partial dates will be as follows:

- Missing days will default to the first of the month for start dates and the last day of the month for stop dates.
- Missing months will default to the first month (January) for start dates and to the last month (December) for stop dates.
- There will be no default for a missing year field.

In the case where it is impossible to define an AE as treatment-emergent or not, the AE will be classified by the worst case assigned, i.e. a TEAE.

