12.6.1.4. Pre-treatment Adverse Event

An AE with a start date and time before the first dose of study drug.

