12.6.1.5. Treatment-Emergent Adverse Event

An AE with a start date and time on or after the first dose of study drug.

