12.6.2. Adverse Event Collection, Assessment and Reporting

12.6.2.1. Observation Period for Assessment of Adverse Events

For the purposes of this study, the period of observation for collection of AEs (including nonserious AEs and SAEs) extends from the time the participant begins study treatment (Day 1) until the EOS visit (within 2-11 days after last administration of the study drug). If a participant withdraws or is discontinued from the study by the Investigator, AEs should be collected from the time the participant begins study treatment (Day 1) up to the completion of EOS assessments.

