12.6.2.2. Parameters for Adverse Events Collection

All nonserious AEs and SAEs will be recorded on the AE eCRF. SAEs will also be immediately reported to the Sponsor safety representative in accordance with Section [12.5.5](#).

Nonserious and SAEs will be documented in the clinical database with the highest severity documented during the duration of each serious or nonserious episode. Each AE is to be documented in the eCRF with reference to date of onset, severity, relationship to study drug, treatment of event, and outcome.

All AEs are to be followed up until resolution or a stable clinical endpoint is reached, as determined by the Investigator. Changes in AEs and resolution dates are to be documented in the eCRF.

Participants will be instructed by the Investigator to report AEs at each study visit. All volunteered, elicited, and observed AEs are to be recorded. A consistent methodology of nondirective questioning should be adopted for eliciting AE information at all participant evaluation timepoints. Examples of nondirective questions include the following:

- “How are you feeling?”
- “How have you felt since your last clinic visit?”

- “Have you had any new or changed health problems since you were last here?”
- “Have you taken any new medications since your last visit?”

The following considerations should also be made regarding AE and SAE reporting:

- All medical and psychiatric conditions present at screening (i.e., conditions present before the AE reporting period) will be considered preexisting conditions and documented in the medical history eCRF. A preexisting condition is not to be reported as an AE. If a preexisting condition worsens during the study treatment period, the event should be reported as an AE. Planned hospitalization for a preexisting condition, or a procedure required by the protocol, without serious deterioration in health, is not considered an SAE.
- Diagnostic and therapeutic noninvasive and invasive procedures, such as surgery, should not be reported as AEs. A medical condition for which an unscheduled procedure was performed, should however be reported if it meets the definition of an AE. For example, an acute appendicitis, and not the appendectomy, should be reported as the AE.

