14.5. Safety Analysis

All analyses of safety will be conducted on the Safety Population unless otherwise specified in the SAP.

All reported AEs will be graded using NCI CTCAE version 5.0 and will be coded using the Medical Dictionary for Regulatory Activities, version 26.0. The incidence of treatment-emergent AEs (TEAEs) will be included in incidence tables. Events with missing onset dates will be included as treatment-emergent. If a participant experiences more than 1 occurrence of the same AE, the occurrence with the greatest severity and the closest association with the study treatment will be used in the summary tables. All TEAEs will be summarized by treatment group (NKF-INS(A), US-NovoLog®, and EU-NovoRapid®) as follows:

- All AEs
- Grade ≥ 3 AEs
- AEs related to study treatment, including related Grade ≥ 3 AEs
- All adverse reactions
- SAEs

All AEs will be listed by participant, along with information regarding onset, duration, relationship and severity to study treatment, action taken with study treatment, treatment of event, and outcome.

Clinical laboratory data (hematology, clinical chemistry [including glucose], coagulation, and urinalysis) and vital signs (heart rate, respiratory rate, systolic and diastolic blood pressure, and temporal or ear temperature measurements) will be summarized by treatment group and

scheduled visits using descriptive statistics, including mean values and mean change from screening values, as well as numbers of participants with values outside limits of the normal range at each timepoint. Shift tables will be provided presenting change from screening values to the last EOS visit.

The frequency of ECG abnormalities (e.g., heart rate, PR interval, QRS complex, and QT-interval corrected by Fridericia's formula [Fridericia's corrected QT]) will be summarized by treatment group and scheduled visits using counts and percentages.

Participant ECG status (normal, abnormal clinically significant, or abnormal not clinically significant) may be summarized for each scheduled ECG and shifts from screening may be tabulated.

Injection site reactions will be summarized by treatment group and scheduled visits. The number and percentage of participants having reactions at each assessment timepoint, overall and by specific reaction subtype, will be presented.

Summary tables will be provided for concomitant medications initiated during the study period.

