### 18.2.3 Drug-related TEAEs

Classification of Adverse Events by relationship to study treatment:

- **NOT RELATED:** There is not a reasonable possibility that the administration of the study intervention caused the event, there is no temporal relationship between the study intervention and event onset, or an alternate etiology has been established.
- **RELATED:** The AE is known to occur with the study intervention, there is a reasonable possibility that the study intervention caused the AE, or there is a temporal relationship between the study intervention and event. Reasonable possibility means that there is evidence to suggest a causal relationship between the study intervention and the AE.

The incidence of all drug-related TEAEs will be presented by SOC and preferred term for each treatment of event. “*Treatment of event*” will be derived as the last treatment exposed to prior to the onset of the AE.

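### SAP 18.1 and 18.2.3 misplace two kinds of edge-case AE in the by-product safety tables: AEs with partial start dates and AEs that worsen after a dose

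*SAP*

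**What the plan says.** **TEAE definition.** Protocol 12.6.1.5 uses onset alone: "An AE with a start date and time on or after the first dose of study drug". SAP 18.1 adds a worsening limb: "as well as those events that started prior to the first study drug administration, but which worsened after the first study drug administration". Protocol Section 14 lets the SAP prevail where the two differ.

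**Partial dates.** SAP 18.1 imputes whenever at least the year is known: "Missing days will default to the first of the month for start dates", and a missing month becomes January. It also classes an AE as a TEAE where its status cannot be determined, but does not say whether that is judged before or after imputation. Protocol 14.5 is conservative: "Events with missing onset dates will be included as treatment-emergent". SAP 7.1 says missing safety data are not imputed and that incomplete dates are left as they are.

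**Product.** SAP 18.2.3 says treatment of event "will be derived as the last treatment exposed to prior to the onset of the AE". The TEAE tables in SAP 18.2.1 to 18.2.6, including those by severity, use this variable. Protocol 12.6.2.2 records each episode at its highest severity.

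**Collection.** Protocol 12.6.2.1 says AE collection "extends from the time the participant begins study treatment (Day 1) until the EOS visit". Protocol 12.6.1.4 nevertheless defines a pre-treatment AE: "An AE with a start date and time before the first dose of study drug". Protocol 9.1.3 makes illnesses first occurring during the study AEs, and 7.3 asks for any SAE in screen failures. Protocol 12.6.2.2 adds: "If a preexisting condition worsens during the study treatment period, the event should be reported as an AE".

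**The concern.** AE counts by product are the safety comparison in this crossover. Safety is a secondary objective, and Protocol 4.1 states that this is the first clinical study of the test product. Each AE needs two derived facts: whether it is treatment-emergent, and which product it belongs to. Both depend on the start date.

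The start-date default only ever moves an event backward in time. Backward means out of the TEAE tables or towards an earlier product, although both documents intend doubtful events to be counted. The attribution rule looks only at onset, so it takes no account of the dose that preceded a worsening, even though worsening is what brings some events into the TEAE definition.

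**Working it through.** The documents give no figure to reproduce. I checked the rules against one another and enumerated dates for the partial-date rule.

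**1. Partial dates: the logic**

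Let d1 be the first-dose date, and let an AE on or after d1 have its day missing. The imputed start is the first of the onset month.

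- It falls before d1 when the AE is in the first-dose month and d1 is not the 1st.
- Otherwise it is on or after d1, but falls in an earlier period whenever a later dose lies between the first of the month and the true onset.

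Example A: first dose 10 March, AE on 12 March recorded as March. The imputed start is 1 March, so the AE is pre-dose: not a TEAE on its start date, and with no prior product.

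Example B: first dose 20 March, period 2 dose on Day 17 (20 March + 16 days = 5 April), AE on 10 April recorded as April. The imputed start is 1 April, so the AE goes to the period 1 product.

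The worst-case clause does not clearly rescue Example A. Imputation runs whenever the year is known, so afterwards status can be determined; the clause would then reach only AEs with a missing year.

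**2. Partial dates: the size**

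Inputs from SAP Table 6.1:
- shortest schedule: dosing on Days 1, 6 and 13, post-study visit on Day 16
- longest schedule: dosing on Days 1, 17 and 40, post-study visit on Day 52

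Assumptions, which are mine: first dose uniform over a 365-day year, onset uniform from Day 1 to the post-study visit, defaults applied before the worst-case clause.

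For every pair of first-dose date and onset day, I compared the imputed start with the dosing dates.

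| Day missing | Shortest | Longest |
|---|---|---|
| Pairs | 365 × 16 = 5,840 | 365 × 52 = 18,980 |
| Moved before first dose | 4,208 (72%) | 5,373 (28%) |
| Still post-dose, earlier product | 996 (17%) | 7,571 (40%) |
| Correct product kept | 636 (11%) | 6,036 (32%) |

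With both day and month missing (imputed to 1 January), 98% and 93% fall before first dose.

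These are shares of AEs with partial dates, not of all AEs. The documents give no expected number of AEs with partial dates.

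**3. Worsened events**

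- Onset before first dose, worse afterwards: a TEAE under SAP 18.1. If it keeps its pre-dose onset, no treatment precedes it, so SAP 18.2.3 returns nothing and it has no column in the tables.
- Mild after the Day 1 dose, Grade 3 after a period 2 dose on Day 6: Protocol 12.6.2.2 makes this one record at Grade 3. SAP 18.2.3 credits it to the period 1 product. The washout before period 2 can be as short as 3 days, so an event spanning two doses is plausible.

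**4. Consistency**

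- SAP 7.1 and SAP 18.1 give opposite instructions on incomplete dates.
- Protocol 12.6.2.1 starts collection at Day 1 dosing, while 12.6.1.4, 9.1.3 and 7.3 presuppose some recording before it.

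**The case against.** A reader might infer that the TEAE rules cannot be applied at all. The documents do not support that: an AE with a complete post-dose onset that does not worsen across a later dose gets one status and one product.

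A reader might also infer that pre-dose events are never collected, so that the worsening limb is empty. That goes too far. Protocol 9.1.3 and 12.6.2.2 require worsening of an existing condition, or of an abnormal baseline finding, to be reported as an AE, and medical history is updated at period 1 admission. If the worsening is entered as a new AE, it has a post-dose onset and a product. What stands is that the documents do not say which onset date is entered, and that the provisions on when collection starts conflict.

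On partial dates, the strongest reply is that the worst-case clause may be meant to act on the original partial date, and that with collection starting at dosing, an AE on the form is presumptively post-dose. That order is possible but unstated, and the literal text imputes first. The percentages depend on that order. They also apply to few events: participants are in the unit from Day -1 to Day 2 of each period, onset date is a required AE item, and every AE is still listed.

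**Conclusion.** The point holds for edge cases. Applied as written, SAP 18.1 can move a post-dose AE with a partial date before first dose or to an earlier product, against the conservative intent of SAP 18.1 itself and Protocol 14.5. SAP 18.2.3 gives no product to a worsened event kept with a pre-dose onset, and credits a worsening after a later dose to the earlier product at its highest grade.

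Among day-missing AEs, 72% to 28% (shortest to longest schedule) would fall before first dose and a further 17% to 40% would move to an earlier product. These ranges rest on uniform dates and on imputation being applied first. The number of AEs affected is probably small.

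The conflict over when AE collection starts needs reconciling, but the documents do not show that data will be lost. The effect is confined to the safety tables; the primary PK and PD analyses do not use these rules. The change should be made, because the SAP governs and a few sentences suffice.

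**What to change.** **SAP 18.1.** Judge TEAE status on the original partial date, before any imputation. Class the AE as a TEAE unless the known date parts or the stop date show that it started before first dose and did not worsen afterwards. For these TEAEs, assign the product of the most recent dose compatible with the partial start date and the stop date, flag the record, and impute the start no earlier than that dose.

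A floor at first dose alone is not enough. With doses on 3 and 9 March and an AE on 12 March recorded as March, it would give 3 March and the period 1 product. The most-recent-dose rule is itself a convention and can err towards the later product, which is why the flag is needed.

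**SAP 7.1.** Align it with the revised 18.1.

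**SAP 18.2.3.** For an event that worsens after a dose, derive treatment of event from the date of worsening. Enter the worsening as a new AE record with its own onset date, and adjust the one-severity-per-episode wording in Protocol 12.6.2.2 to match.

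**Protocol 12.6.2.1.** State one start of AE and SAE collection that is consistent with 12.6.1.4, 9.1.3 and 7.3.

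**Cost.** A few sentences in the SAP, a short protocol clarification, and a little more AE recording.
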